5.2 SUBJECT EXCLUSION CRITERIA

We will only exclude those who have opted out of the study and vulnerable patients: those under 21 years of age, prisoners, those with poor cognition or cognitive impairment, and those deemed vulnerable based on cognitive impairment by the Clinical Manager, Medical Director, and/or Social Worker (see Table 3: Screening for Patient Vulnerable Status), and those who are unable to comprehend the patient information sheet due to lack of facility in English or Spanish (patients whose primary spoken language is not English or Spanish). Due to limited availability of peer mentors fluent in languages other than English, only English-speaking patients will be offered peer mentoring.

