Retention of participants in patient activation intervention. While participant retention is an issue in virtually any trial, dialysis patients are likely to experience fatigue, pain and other symptoms; thus there is a greater than average risk of patients not completing the intervention. In the two aforementioned published studies regarding peer mentoring and coaching for hemodialysis patients, participant retention rates were 85.7% for the 2-4 month study and 100% for the 10-week study, respectively.^{18, 153} Another study involving one-to-one peer support to people with diabetes had a 75.7% retention rate for a study that was 8-12 months long.¹⁵⁴ Notably, all of the aforementioned studies were more demanding than ours in terms of numbers of sessions with patients (8-30 sessions). Therefore, based on these prior studies, but recognizing the uncertainties of the COVID-19 pandemic, we estimate a retention rate of at least 73% for the peer mentoring intervention. In summary: if 60 patients in a facility are offered peer mentoring, we predict that approximately 30 of them will agree to receive peer mentoring; of these patients, at least 22 will complete the entire intervention. Under this circumstance, an additional 8 will thus complete part of the intervention.

In order to achieve our estimated retention rate of 65-75% for the complete intervention, and in keeping with published research,¹⁵⁵ our study team will use a combination of retention strategies. The following general evidence-based retention strategies will be used in

combination: patient/community involvement;¹⁵⁶ offering participant incentives;¹⁵⁶ using a participant-tracking database¹⁵⁷; using systematic methods for participant contact and scheduling of peer mentoring appointments;¹⁵⁶ issuing reminders prior to appointments;¹⁵⁶ interpersonal skill training for project staff;¹⁵⁷ monitoring retention;¹⁵⁶ and monitoring satisfaction with the study¹⁵⁸ via the planned peer mentoring survey.

Furthermore, we will follow best practices for retaining older and seriously ill study participants including: demonstrating care for participants by sending birthday or holiday cards;¹⁵⁸ flexibility in scheduling and dividing up peer mentoring sessions over time¹⁵⁸; facilitating home-based participation in the study;¹⁵⁸ developing a protocol for managing missed follow-ups;¹⁵⁸ and keeping response burden for patient data collection very low.¹⁵⁹

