5.4 TREATMENT ASSIGNMENT PROCEDURES

5.4.1 Randomization Procedures

The 20 hemodialysis facilities will be randomized to the four intervention combinations of the 2x2 factorial design, assigning 5 facilities to each of the 4 combinations (both provider education and patient activation using peer mentoring; provider education alone; patient activation alone; and neither intervention). Facilities will be stratified by geographic region and socio-economic status to ensure treatment balance on those factors.

With regard to peer mentoring only, we will randomly select patients who are not vulnerable and have not opted out of the study in succession, until approximately 30 English-speaking patients in a facility accept peer mentoring. Patient randomization will be stratified by treatment shift. Every time a patient declines to participate, we will choose another patient randomly until the enrollment target is reached. Patients entering a facility randomized to the patient activation intervention during weeks 1-18 of the 24-week intervention period will be added to the list of patients eligible for peer mentoring from which patients are randomly selected for peer mentoring. We anticipate that 15-20% of patients in the study facilities will be replaced by new patients during the 11-month study period due to mortality, change in ESRD treatment modality (e.g., a kidney transplant), or changing facilities.

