For the above analyses, the variables of primary interest are the main effects of the interventions. *Session-level* covariate adjustment will include: (1) weekday of session, (2) dialysis session shift, (3) average session blood flow rate; (4) average session dialysate flow rate, and (5) dialysate composition (sodium, potassium, magnesium). *Patient-level* covariate adjustment will comprise: (1) patient demographics (age, race, ethnicity, sex, employment, literacy, education level, language spoken); (2) time since first dialysis; (3) cause of ESRD, (4) treatment history; (5) total transplants; (6) vascular access type; (7) patient laboratory data (serum phosphorous, dialysis adequacy, anemia management (hemoglobin), iron indices (serum ferritin, serum iron), mineral metabolism indices (calcium, phosphate, PTH)); (8) comorbidity index; (9) individual comorbidities and comorbidities in combination, including COVID-19; (10) patient's heart rate variability (based on variability in heart rate (HR) during dialysis session (difference between the highest and lowest heart rates, standard deviation of the heart rate measures, the square root of the mean squared differences of successive heart rate measures); (11) patient medications (prescriptions medications administered outside of center or in-center (including ESA prescription, iron, antibiotics and vitamin D analog), and non-in-center prescriptions). Patient data will be censored while they are at COVID-19 isolation facilities. Regression diagnostics will be used to assess model fit. Checks for functional form of continuous adjustment covariates will be carried out and any transformations will be implemented prior to adding the intervention variables to the model.

Three secondary analyses are planned for this Aim. The first will test the treatment effects in a similar model but adding adjustment for any covariates found to be unbalanced between treatment groups in preliminary analyses. This has the ability to further adjust for important confounders of treatment effects, but because it will use data-driven covariate decisions that are subject to analysis bias, it will be interpreted with caution. The next secondary analysis will test the interaction between the two interventions to detect a possible synergistic or antagonistic

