We will compare the characteristics of those with missing data to those without missing data, to test whether characteristics are similar between the groups (see Preliminary Data Analysis) (MD-2). In addition to complete case analyses, we will use state-of-the-art statistical methods such as likelihood approaches and multiple imputation to deal with missing data (MD-3).¹⁶⁰ These sensitivity analyses will assess the robustness of the results to missing data (MD-5).

Heterogeneity of Treatment Effect Analyses (HT-2; Moderation). The primary analysis will examine average treatment effects (ATE), but we will also examine heterogeneity of treatment effects (HTE) on HD session instability (IDH) rate for a variety of covariates, particularly those that are characterized by differential outcomes among HD patients (HT-1). Covariates of interest for HTE analyses include: age, race,¹⁶³, ethnicity, level of education¹⁶⁴, literacy, presence of comorbidities, and heart rate variability (HT-4). Supporting these HTE analyses, greater benefits from peer mentoring for African Americans were found in a trial conducted by our advisory partner, NKFM.¹⁸ Depending on sample sizes obtained for each of the covariates of interest, either a subgroup analysis or an analysis including interaction terms will be employed to examine HTE (HT-3). Only two-way interactions between the treatment indicator and each of the covariates will be analyzed. There may be different moderators for the two interventions.

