In both Aims 1 and 2, the primary results will be based on the treatment effects tested in the initial models described for CRCTs with pre-planned covariates. Depending on the specific outcome, covariate adjustment for these analyses will include: (1) patient demographics (age, race, ethnicity, sex, employment, literacy, education level, language spoken), (2) time since first dialysis, (3) cause of ESRD, (4) treatment history, (5) total transplants, (6) vascular access type, (7) patient laboratory data (serum phosphorous, dialysis adequacy, anemia management (hemoglobin), iron indices (ferritin, serum Iron), mineral metabolism indices (calcium, phosphate, PTH)); (8) comorbidity index; (9) individual comorbidities and comorbidities in combination, including COVID-19; (10) patient's heart rate variability for the whole session or up until IDH occurs (if IDH occurs) (based on variability in heart rate (HR) during dialysis session (Difference between the highest and lowest heart rates, standard deviation of the heart rate measures, the square root of the mean squared differences of successive heart rate measures)); and (11) patient medications (prescriptions medications administered outside of center or in-center (including ESA prescription, iron, antibiotics and vitamin D analog)). Intent-to-treat analyses will be carried out, which means that any deviations from the randomized interventions will not be taken into account in the primary test of treatment effects. Additionally, we will conduct as-treated analyses for the peer mentoring intervention whereby only patients who received peer mentoring are compared to patients in the other treatment arms, with adjustment for the same factors as in the intent-to-treat analyses. The small number of facilities (20) will preclude post-hoc adjustment for facility non-compliance with the interventions.

Heterogeneity of Treatment Effect Analyses (Moderation). As with the primary outcome analyses, the following potential moderators will be assessed: 1) patient demographics, including age, race, ethnicity, literacy, and education level; (2) comorbidities; and (3) heart rate variability.

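### For peer mentoring, a smaller effect in Hispanic patients could come from the English-only offer rule, and no planned analysis would separate that from a weaker response

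*Combined protocol and SAP*

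**What the plan says.** Three parts of the combined protocol and SAP bear on this.

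*Who is in the study.* Section 5.2 excludes "those who are unable to comprehend the patient information sheet due to lack of facility in English or Spanish". A patient who understands Spanish but not English is therefore enrolled and analysed, whatever the arm. Section 2.2.2 and Table 3 in section 7.1 agree.

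*Who can be offered mentoring.* Section 5.2 goes on: "Due to limited availability of peer mentors fluent in languages other than English, only English-speaking patients will be offered peer mentoring". Section 5.4.1 fills the facility quota by random selection "until approximately 30 English-speaking patients in a facility accept peer mentoring".

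*What is tested.* For the primary outcome, the heterogeneity paragraph of section 11.4 names age, race, ethnicity, education, literacy, comorbidities and heart rate variability. Each is to be examined by subgroup analysis or by an interaction term, depending on numbers, and "Only two-way interactions between the treatment indicator and each of the covariates will be analyzed". The matching paragraph for Aim 2 lists "patient demographics, including age, race, ethnicity, literacy, and education level", plus comorbidities and heart rate variability. Language appears only among the adjustment covariates of the outcome models ("employment, literacy, education level, language spoken").

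**The concern.** The ethnicity moderation analysis is run in everyone enrolled, but part of one ethnic subgroup may be closed to mentoring by a rule that exists because few mentors speak other languages. If mentoring worked equally well in everyone who could be offered it, the subgroup containing ineligible patients would still show a smaller average effect.

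Adjusting for language does not help. A language main effect shifts the expected outcome by the same amount in mentoring and non-mentoring facilities, whereas the artefact lies in the treatment-by-language term, which is not in the model.

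What is at stake is interpretation. Section 2.1.2 presents peer mentoring as an approach that can work in Hispanic patients and notes that they are overrepresented on hemodialysis. A reported ethnicity interaction could be taken to contradict that when the cause is mentor supply. Only the patient activation factor is affected, because the provider intervention reaches all patients in its facilities.

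**Working it through.** **Inputs from section 11.2.** Effect D = 0.034 to 0.043, SD = 0.08 to 0.10, ICC = 0.10, 60 patients per facility, 10 facilities per level of each factor (600 patients per level), alpha 0.05.

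**Inputs not in the documents, so assumed.** Hispanic share h = 15-25%; share of Hispanic patients who do not speak English s = 20-50%; all other patients speak English; the Hispanic share is the same in every facility.

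**Step 1: reproduce Table 5.** Design effect = 1 + 59 x 0.10 = 6.9. SE = SD x sqrt(2 x 6.9 / 600), which is 0.01213 for SD 0.08 and 0.01517 for SD 0.10. Power = Phi(D/SE - 1.96).

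| D | SD | Recomputed | Table 5 |
|---|---|---|---|
| 0.034 | 0.08 | 80.0% | 80% |
| 0.034 | 0.10 | 61.1% | 61% |
| 0.040 | 0.08 | 90.9% | 91% |
| 0.043 | 0.10 | 80.9% | 81% |

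The plan's inputs reproduce its own figures, so they can be carried forward.

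**Step 2: the artificial interaction.** Let D be the intent-to-treat effect among patients who can be offered mentoring, and p the fraction of it that reaches patients who cannot (spillover). The Hispanic subgroup shows D(1 - s) + D x s x p and the comparison subgroup shows D. The difference is d = D x s x (1 - p). With D = 3.4 points and p = 0, d = 3.4 x 0.20 = 0.68 to 3.4 x 0.50 = 1.70 points.

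**Step 3: its standard error.** Ethnicity varies within facilities, so with equal shares the facility variance cancels: SE = sqrt(0.9 x SD^2 x (2/nH + 2/nN)), with nH = 600h and nN = 600(1 - h).

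**Step 4: rejection rate with no true difference among eligible patients.** Phi(d/SE - 1.96) + Phi(-d/SE - 1.96), for p = 0:

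| h (nH / nN) | SD | SE (points) | s = 20%, d = 0.68 | s = 50%, d = 1.70 |
|---|---|---|---|---|
| 15% (90 / 510) | 0.08 | 1.23 | 8.6% | 28.3% |
| 15% (90 / 510) | 0.10 | 1.53 | 7.3% | 19.8% |
| 25% (150 / 450) | 0.08 | 1.01 | 10.3% | 39.0% |
| 25% (150 / 450) | 0.10 | 1.27 | 8.4% | 26.9% |

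**Step 5: weaker assumptions.**
- Half spillover (p = 0.5): d = 0.34 to 0.85 points, rejection about 6-13%.
- Effect halved to 1.7 points, for example because, of 60 patients offered mentoring, "approximately 30 of them will agree to receive peer mentoring" (section 5.3): the same d, so again about 6-13%.
- Both together: about 5-7%.
- Uneven shares, as an illustration: 2 of 10 facilities 85% Hispanic and 8 at 10%, still 25% overall. Within-facility information, the sum of 60h(1 - h), falls from 10 x 60 x 0.25 x 0.75 = 112.5 to 2 x 7.65 + 8 x 5.40 = 58.5. SE = sqrt(0.9 x 0.08^2 x 2/58.5) = 1.40 points, and the 39% becomes about 23%.

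**Step 6: restriction to English speakers.** Now s = 0 in the analysed sample, so d = 0 by construction. The price is precision: nH becomes 600h(1 - s). The SE ratio is smallest at h = 25%, s = 20%: sqrt((2/120 + 2/450) / (2/150 + 2/450)) = 1.09. It is largest at h = 15%, s = 50%: sqrt((2/45 + 2/510) / (2/90 + 2/510)) = 1.36.

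**The case against.** The best defence is that this is a pragmatic, facility-level trial. A programme that reaches fewer Hispanic patients does have a smaller effect in that group, and the all-patient estimate says so correctly. That stands. A reader might infer that the planned moderation estimate is wrong and should be replaced; the documents do not support that. The error would arise only if the estimate were read as a weaker response to mentoring.

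The plan is also not blind to limited reach. Sections 2.2.3 and 11.1 expect some patients to refuse or be unable to take part, and promise to explore this through sensitivity, mediation and moderation analyses. Section 11.4 leaves its moderator list open and allows the two interventions to have different moderators. These statements make a language analysis easy to add, but none specifies one. The as-treated analysis compares mentored patients with the other arms without limiting the comparators to English speakers. The compliance sensitivity analysis concerns acceptance, not eligibility.

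Section 4.1 expects unmentored patients may gain by passive exposure. That would shrink the artefact, and would remove it only if spillover were complete.

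Three stronger readings are tempting. One is that moderation by literacy and education is distorted too; that requires them to track language, and no section shows it. Another is that all Spanish speakers are barred; a bilingual patient who speaks English can be offered mentoring. The third is that the investigators will misread the result; nothing in the documents says how they would interpret it.

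**Conclusion.** The point holds as a gap in interpretation. For the patient activation factor, the plan cannot distinguish a weaker response among Hispanic patients from the English-only offer rule, and adjusting for language as a main effect does not supply the distinction.

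Unless spillover is complete, the direction is fixed for any subgroup containing a larger share of patients who do not speak English. That Hispanic patients are such a subgroup is a reasonable inference; the documents give no figure. The size is unknown. The 0.7-1.7 point interaction and 7-39% rejection rate depend on assumed shares, equal shares across facilities and no spillover. The upper end is the corner with the largest shares and smallest SD. Half spillover or a halved effect gives about 6-13%, and both together 5-7%, close to nominal.

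Severity is minor. These are secondary moderation analyses with no stated power, for one of two factors. The primary intent-to-treat result and all provider education analyses are unaffected.

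**What to change.** In section 11.4, under both heterogeneity paragraphs:

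- Keep the all-patient moderation analysis, labelled as the effect of the programme as delivered.
- For the mentoring factor, add a companion moderation analysis and a companion main-effect estimate in English-speaking patients of all four arms.
- Define English-speaking from the recorded baseline language field, in the same way in mentoring and non-mentoring facilities, so that the randomised comparison is preserved.
- Report the number not eligible for mentoring in each ethnic subgroup.
- State that an ethnicity interaction will not be interpreted as differential response unless it also appears in the restricted analysis, judged on the estimate and its interval as well as the p-value.

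The cost is a few sentences and a small number of extra model runs. Under the shares assumed above, the restriction drops 3% (0.15 x 0.20) to 12.5% (0.25 x 0.50) of patients and widens the interaction standard error by 9-36%. It removes the eligibility artefact only, not differences in acceptance. It also says nothing about patients who do not speak English, which is why the all-patient analysis stays.

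One point to check before adoption: eligibility is stated as speaking English, the covariate is language spoken, and Table 3 refers to primary spoken language. If the field records only primary language, some bilingual patients who could be offered mentoring would be misclassified.

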16% in the intervention group. It is assumed that a minimum of 60 hemodialysis patients will be observed for at least 60 dialysis sessions and the outcome will be the proportion of unstable sessions, which we treat as a continuous variable. These proportions among patients in a facility are assumed to be normally distributed with mean 0.20 in the control group and mean between 0.16 and 0.17 in the intervention group (a difference, d , of 0.034 to 0.043), with standard deviation (SD, or 'sigma') assumed to be in the range 0.08 to 0.10. We conservatively assume $n=60$ patients per facility, i.e., a total of $60 \times 20 = 1,200$ patients. The power calculation is robust to changes in number of patients (m), as the calculation of K (number of clusters) only increases by ~ 1 if m is increased to 90. The intraclass correlation coefficient for hemodialysis facilities is assumed to be 0.10. A significance level of 0.05 was assumed in all calculations. Table 5 gives the statistical power to detect a given difference (D , 0.034-0.043), with sigma values of 0.08 and 0.10, and number of clusters (dialysis units, k) per treatment group of 10 (20 facilities total).

Table 5 shows that detecting a difference of ~ 0.03 (i.e., 20% versus 17% of sessions unstable) with 80% power is only feasible with a SD (sigma) of 0.08 or less. If the standard deviation is as large as 0.10, we can detect a difference of 0.043 (i.e., 20% vs. 16%) with 81% power. Put another way, if the smallest variance estimate is correct ($\sigma=0.08$), we have 91% power to detect a 4% difference, and 80% power to detect a 3% difference.

Table 5 - The power is shown to detect a difference in IDH rates (D) between groups assuming 3 possible standard deviations (sigma). The minimum number of facilities (K) is also shown, illustrating some flexibility to accommodate drop-out. Bolded cells show power $\geq 80\%$.						
D	0.034	0.034		0.040	0.043	
Sigma	0.08	0.10		0.08	0.10	
K	10	10		10	10	
Power	80%	61%		91%	81%	

II. Secondary Outcomes

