Mediation Analyses. The second part of these analyses aim to identify mechanisms of action for the interventions, such as changes in patient or practitioner behavior and session characteristics; these changes in behavior will identify important pathways for improvement in reducing IDH. However, these analyses are not intended to be used for causal inferences. The basic mediation analysis involves 3 steps: (1) confirm that the intervention predicts the outcome (and if not, then mediation analysis is not relevant), (2) confirm that the intervention predicts the mediator (i.e., that the intervention has resulted in specific changes in patient or practitioner behavior; if not, then the potential mediator cannot mediate an intervention effect), and (3) in a model predicting the outcome with covariates including both the intervention and the mediator, confirm that the intervention effect has been reduced after adding the mediator to the model, and confirm that the mediator is a statistically significant predictor of the outcome. The role of moderation in a mediation analysis can also be tested. Each potential mediator is tested

separately, without adjusting for other mediators, although associations between mediators can separately be assessed for improved interpretation.

Mediators of the Primary Outcome: The following variables will be examined as potential mediators of the treatment effect on the primary outcome of dialysis session stability:

Patient-level variables: (1) patient session instability prevention behavior; (2) fluid management practice patterns; (3) number and categories of BP medications patient is taking; (4) fluid adherence (inter-dialytic weight gain); (5) dialysis adherence; (6) patient symptoms (symptom burden measure and recovery time); (7) hospitalizations for cardiovascular or fluid-related causes; and (8) quality of life.

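### The mediation steps turn a failed facility-level test into a statement that a variable cannot mediate, or that mediation is not relevant, although Table 5 implies that step 1 alone would miss a real pathway in 9% to 39% of trials

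*Combined protocol and SAP*

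**What the plan says.** Section 11.4, Mediation Analyses under Aim 1, describes three steps.

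- **Step 1** asks whether the intervention predicts the outcome, "and if not, then mediation analysis is not relevant".
- **Step 2** asks whether the intervention predicts the mediator; "if not, then the potential mediator cannot mediate an intervention effect".
- **Step 3** puts intervention and mediator in one model, looks for a smaller intervention effect, and asks the analyst to "confirm that the mediator is a statistically significant predictor of the outcome".

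Statistical significance is named only in step 3; steps 1 and 2 give no criterion. No estimate or interval for an indirect effect is planned. The section says that "these analyses are not intended to be used for causal inferences", but it also gives its aim as finding the interventions' mechanisms of action. Section 11.1 relies on mediation, among other analyses, to explain any differential improvement.

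The Aim 2 part of Section 11.4 plans mediation for six secondary outcomes and describes no other method. Section 11.2 states that the study was not powered specifically for the secondary outcomes.

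For the primary outcome, Section 11.2 says: "A significance level of 0.05 was assumed in all calculations". It adds: "If the standard deviation is as large as 0.10, we can detect a difference of 0.043", with 81% power. Table 5 gives power of 80%, 61%, 91% and 81%.

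**The concern.** A variable that the intervention truly does not move cannot carry its effect. The plan applies that statement to something else: a variable for which an effect was not confirmed on 20 facilities. There is no margin, no interval and no middle category, so an underpowered step 2 is written up as a negative finding about mechanism. Step 1 is milder in wording, but it closes the formal mediation analysis on the same kind of evidence.

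The stake is interpretation after a null or borderline IDH result. The team would then want to separate an intervention that did not change the intermediate steps from one that changed them without affecting IDH. As written, the mediation models would not be fitted. For any variable that fails step 2, readers would be told that the pathway cannot operate.

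**Working it through.** **Inputs (Section 11.2).** 10 facilities per group in each main-effect comparison; 60 patients per facility; ICC 0.10; SD 0.08 or 0.10; D from 0.034 to 0.043; alpha 0.05. Sidedness is not stated for the primary outcome; two-sided reproduces Table 5.

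**Reproducing Table 5.** Design effect = 1 + (60 − 1) × 0.10 = 6.9. Effective n per group = 600 / 6.9 = 86.96. SE = SD × √(2 / 86.96), which is 0.01213 at SD 0.08 and 0.01517 at SD 0.10. Power = Φ(D/SE − 1.96).

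| D | SD | D/SE | Power, recomputed | Table 5 | Step 1 miss rate | Miss rate, t on 18 df |
|---|---|---|---|---|---|---|
| 0.034 | 0.08 | 2.80 | 80.0% | 80% | 20% | 24% |
| 0.034 | 0.10 | 2.24 | 61.1% | 61% | 39% | 44% |
| 0.040 | 0.08 | 3.30 | 90.9% | 91% | 9% | 12% |
| 0.043 | 0.10 | 2.84 | 80.9% | 81% | 19% | 24% |

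Table 5 therefore uses the normal approximation. The miss rate is 1 − power. Power with t on 18 df is 75.5%, 56.4%, 87.6% and 76.5%.

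**Adding step 2.** Weight gain is both a listed mediator and the outcome in Table 6, so Table 6 gives its step 2 power. Treating the two tests as independent (an assumption), the share missed is 1 − p1 × p2:

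- 1 − 0.91 × 0.99 = 10%
- 1 − 0.91 × 0.91 = 17%
- 1 − 0.80 × 0.91 = 27%
- 1 − 0.61 × 0.68 = 59%
- 1 − 0.61 × 0.36 = 78%

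Without independence, the share missed is at least the larger of the two single-step miss rates.

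**Secondary outcomes.** The lowest tabulated power is 0.36 for weight gain (Table 6), 0.40 for recovery time (Table 7) and 0.49 for symptom burden (Table 8). Step 1 would close those analyses in 64%, 60% and 51% of trials in those scenarios.

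**What step 1 protects against.** Mediators are not randomised. Take a 0.5 SD shift in the mediator, no true mediator effect, no total effect, and a residual patient-level mediator–outcome correlation of 0.1. The shift and the correlation are assumptions, not figures from the plan.

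- Step 2 power with t on 18 df is 0.876 at mediator ICC 0.1 and 0.629 at 0.2.
- Step 3, approximated by the within-facility slope with about 1,180 degrees of freedom, has z ≈ 0.1 × √1180 = 3.44, so power ≈ Φ(3.44 − 1.96) = 0.93.
- The products are 0.876 × 0.93 = 0.81 and 0.629 × 0.93 = 0.58.

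Simulation under the same assumptions gave 82% and 59%. With step 1 kept, a false pathway was declared in about 1% to 2% of trials.

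**The case against.** The strongest reply is that step 1 limits scope and makes no claim of absence: with no demonstrated effect, the plan chooses not to explain one. That is a fair reading of step 1. Only step 2 says that a variable cannot mediate.

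The second reply is that the step 1 gate does useful work, and the calculation above supports it. A reader might infer that dropping step 1 is harmless because false positives stay near 4% to 5%. That holds only without mediator–outcome confounding. Modest confounding raises the rate to roughly 60% to 82%. Covariate adjustment may reduce this, but it cannot be assumed to remove it. So steps 2 and 3 alone must not be used to declare a pathway.

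Third, a reader might infer that the gate throws away the evidence on whether practice changed. The documents do not support that. Weight gain is a secondary outcome with its own comparison (Sections 3.2.2 and 11.4). Treatment time and ultrafiltration rate are components of the fluid practice patterns measure, listed as a behavioral outcome (Sections 3.2.3 and 4.1). The Practice Patterns survey covers all facilities (Section 10.1). Only the formal mediation models are lost.

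Finally, the analyses are labelled non-causal, and stepwise testing is partly a choice of method. Both points limit the weight of the concern. Neither justifies wording that turns a failed confirmation into an impossibility.

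**Conclusion.** The point stands for the decision rule. Failure to confirm step 2 is read as showing that a variable cannot mediate, and failure at step 1 ends the analysis, on 20 facilities and with no interval. On Table 5, step 1 alone would stop the analysis of a real pathway in 9% to 39% of trials (12% to 44% with t on 18 df), before any loss at step 2.

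A reader might take 20% as the floor. It is the lower value only for the two D = 0.034 columns, where the range is 20% to 39%; the other two columns give 9% and 19%.

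The figures rest on three assumptions: confirmation means p<0.05, the true total effect equals the tabulated D, and each intervention is judged on its own main effect. A pathway with a smaller total effect would be missed more often. If p<0.05 is not meant, steps 1 and 2 have no criterion, which also needs correcting. The primary and secondary treatment-effect tests are unaffected.

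**What to change.** In Section 11.4, replace the conclusion that a variable cannot mediate with: not shown to be a mediator (inconclusive). State the criterion for steps 1 and 2.

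For each pre-listed mediator that is not part of the outcome definition (the lowest SBP reading, for example, is part of it), report these with 95% intervals from facility-level inference, whatever the total-effect p-value:

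- the intervention-to-mediator effect;
- the mediator-to-outcome association adjusted for intervention;
- their product.

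Label all of them exploratory and open to mediator–outcome confounding. Keep the statement that they are not for causal inference. Do not declare a pathway established when the total effect is not shown. Apply the same wording to the Aim 2 mediation analyses.

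The cost is SAP wording and modest programming, with no new data. The downside is more exploratory output: the primary outcome has 8 + 14 = 22 listed mediators and two interventions, so up to 44 sets of estimates before the exclusion above.
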